10.1.4 Data protection

UCB staff (or designee) will affirm and uphold the participant's confidentiality. Throughout this study, all data forwarded to UCB (or designee) will be identified only by the participant number assigned at Screening.

The Investigator agrees that representatives of UCB, its designee, representatives of the relevant IRB/IEC, or representatives of regulatory authorities will be allowed to review that portion of the participant's primary medical records that directly concerns this study (including, but not limited to, laboratory test result reports, ECG reports, admission/discharge summaries for hospital admissions occurring during a participant's study participation, and autopsy reports for deaths occurring during the study).

The participant must be informed that his/her personal study-related data will be used by the Sponsor in accordance with local data protection law. The level of disclosure must also be explained to the participant.

The participant must be informed that his/her medical records may be examined by Clinical Quality Assurance auditors or other authorized personnel appointed by the Sponsor, by appropriate IRB/IEC members, and by inspectors from regulatory authorities.

10.1.5 Committees structure

An IDMC will review the safety and tolerability data in this study in order to make recommendations for the Sponsor.

An IDMC will be set up in line with the FDA regulatory requirements and EMA Guideline on IDMCs (EMA/CHMP/EWP/5872/03 Corr, adopted 27/05/2005). The IDMC will consist of external experts who are independent from UCB and the clinical operations contract research organization, and have no conflict of interest related to the conduct or the outcomes of the study.

10.1.6 Data quality assurance

All participant data relating to the study will be recorded on printed or eCRF unless transmitted to the Sponsor or designee electronically (eg, laboratory data). The Investigator is responsible for verifying that data entries are accurate and correct by physically or electronically signing the eCRF.

The Investigator must maintain accurate documentation (source data) that supports the information entered in the eCRF.

The Investigator must permit study-related monitoring, audits, IRB/IEC review, and regulatory agency inspections and provide direct access to source data documents.

The Sponsor or designee is responsible for the data management of this study including quality checking of the data.

Study monitors will perform ongoing source data verification to confirm that data entered into the eCRF by authorized site personnel are accurate, complete, and verifiable from source documents; that the safety and rights of participants are being protected; and that the study is being conducted in accordance with the currently approved protocol and any other study agreements, ICH-GCP, and all applicable regulatory requirements.

All essential documents are to be retained by the Investigator until at least 2 years after the last approval of a marketing application in an ICH region and until there are no pending or contemplated marketing applications in an ICH region, or at least 2 years have elapsed since the formal discontinuation of clinical development of the study medication/investigational device. These documents should be retained for a longer period, however, if required by the applicable regulatory requirement(s) or by an agreement with UCB (Committee for Proprietary Medicinal Products [CPMP]/ICH/135/95, 2002 [Section 4.9.5]). The Investigator will contact UCB for authorization prior to the destruction of any study records or in the event of accidental loss or destruction of any study records. The Investigator will also notify UCB should he/she relocate or move the study-related files to a location other than that specified in the Sponsor's trial master file.

10.1.6.1 Electronic Case Report form completion

The Investigator is responsible for prompt reporting of accurate, complete, and legible data in the eCRFs and in all required reports.

Any change or correction to the eCRF after saving must be accompanied by a reason for the change.

Corrections made after the Investigator's review and approval (by means of a password/electronic signature) will be reapproved by the Investigator.

The Investigator should maintain a list of personnel authorized to enter data into the eCRF.

Detailed instructions will be provided in the eCRF Completion Guidelines.

10.1.6.2 Apps

Not applicable.

10.1.7 Source documents

All source documents must be accurate, clear, unambiguous, permanent, and capable of being audited. They should be made using some permanent form of recording (ink, typing, printing, optical disc). They should not be obscured by correction fluid or have temporary attachments (such as removable self-stick notes). Photocopies and/or printouts of eCRFs are not considered acceptable source documents.

Source documents are original records in which raw data are first recorded. These may include hospital/clinic/general practitioner records, charts, diaries, x-rays, laboratory results, printouts, pharmacy records, care records, ECG or other printouts, completed scales, quality of life questionnaires, or video, for example. Source documents should be kept in a secure, limited access area.

Source documents that are computer generated and stored electronically must be printed for review by the monitor (eg, ECG reports). Once printed, these copies should be signed and dated

by the Investigator and become a permanent part of the participant's source documents. The Investigator will facilitate the process for enabling the monitor to compare the content of the printout and the data stored in the computer to ensure all data are consistent.

Electronic data records, such as Holter monitor records or electroencephalogram records, must be saved and stored as instructed by UCB (or designee).

10.1.8 Study and site closure

The Sponsor/designee reserves the right to close the study site or terminate the study at any time for any reason at the sole discretion of the Sponsor. Study sites will be closed upon study completion. A study site is considered closed when all required documents and study supplies have been collected and a study-site closure visit has been performed.

The Investigator may initiate study-site closure at any time, provided there is reasonable cause and sufficient notice is given in advance of the intended termination.

Reasons for the early closure of a study site by the Sponsor or Investigator may include but are not limited to:

- Failure of the Investigator to comply with the protocol, the requirements of the IRB/IEC or local health authorities, the Sponsor's procedures, or GCP guidelines
- Inadequate recruitment of participants by the Investigator
- Discontinuation of further study medication development

10.1.9 Publication policy

The results of this study may be published or presented at scientific meetings. If this is foreseen, the Investigator agrees to submit all manuscripts or abstracts to the Sponsor before submission. This allows the Sponsor to protect proprietary information and to provide comments.

The Sponsor will comply with the requirements for publication of study results. In accordance with standard editorial and ethical practice, the Sponsor will generally support publication of multicenter studies only in their entirety and not as individual site data. In this case, a coordinating Investigator will be designated by mutual agreement.

Authorship will be determined by mutual agreement and in line with International Committee of Medical Journal Editors authorship requirements.

10.2 Appendix 2: Clinical laboratory tests

- The tests detailed in the table below will be performed by the central laboratory.
- Local laboratory results are only required in the event that the central laboratory results are not available in time for either study treatment administration and/or response evaluation. If a local sample is required, it is important that the sample for central analysis is obtained at the same time. Additionally, if the local laboratory results are used to make either a study treatment decision or response evaluation, the results must be entered into the eCRF.
- Protocol-specific requirements for inclusion or exclusion of participants are detailed in Section 5.1 and Section 5.2 of the protocol, respectively.
- Additional tests may be performed at any time during the study as determined necessary by the Investigator or required by local regulations.

Protocol-Required Safety Laboratory Assessments

Laboratory Assessments	Parameters			
Hematology	Platelet Count	RBC Indices:		WBC Count with
	RBC Count	MCV		Differential:
	Hemoglobin	MCH		Neutrophils
	Hematocrit	%Reticulocytes		Lymphocytes Monocytes Eosinophils Basophils
Clinical Chemistry ^a	BUN	Potassium	AST/SGOT	
	Creatinine	Sodium	ALT/SGPT	
	Glucose (fasting)	Calcium	Alkaline phosphatase	
	Lactate dehydrogenase	CRP		
Routine Urinalysis	
 • Specific gravity • pH, glucose, protein, blood, ketones, albumin, bilirubin, urobilinogen, nitrite, leukocyte esterase by dipstick • Microscopic examination (if blood or protein is abnormal) 			
Other Screening Tests	
 • Urine human chorionic gonadotropin pregnancy test (as needed for women of childbearing potential)^b • Serology testing for HIV, hepatitis B, and hepatitis C • All study-required laboratory assessments will be performed by a central laboratory. 			

Laboratory Assessments	Parameters
	
 The results of each test must be entered into the eCRF.

ALT=alanine aminotransferase; AST=aspartate aminotransferase; BUN=blood urea nitrogen; CRP=C-reactive protein; eCRF=electronic Case Report form; HIV=human immunodeficiency virus; IEC=Independent Ethics Committee; IRB=Internal Review Board; MCH=mean corpuscular hemoglobin; MCV=mean corpuscular volume; RBC=red blood cell count; SAE=serious adverse event; SGOT=serum glutamic oxaloacetic transaminase; SGPT=serum glutamic pyruvic transaminase; ULN=upper limit of normal; WBC=white blood cell count

^a Details of liver chemistry stopping criteria and required actions and follow-up assessments after liver stopping or monitoring event are given in Section 7.1.1 and Appendix 6 (Section 10.6). All events of ALT $\geq 3 \times$ ULN and bilirubin $\geq 2 \times$ ULN (>35% direct bilirubin) or ALT $\geq 3 \times$ ULN and INR >1.5, if INR measured, may indicate severe liver injury (possible Hy's Law) and must be reported as an SAE (excluding studies of hepatic impairment or cirrhosis).

^b Local urine testing will be standard for the protocol unless serum testing is required by local regulation or IRB/IEC.

Investigators must document their review of each laboratory safety report.

This document cannot be used to support any marketing authorization application and any extensions or variations thereof.

10.3 Appendix 3: Adverse events – definitions and procedures for recording, evaluating, follow-up, and reporting

10.3.1 Definition of adverse event

AE Definition

- An AE is any untoward medical occurrence in a patient or clinical study participant, temporally associated with the use of study medication, whether or not considered related to the study medication.
- NOTE: An AE can therefore be any unfavorable and unintended sign (including an abnormal laboratory finding), symptom, or disease (new or exacerbated) temporally associated with the use of study medication.

Events Meeting the AE Definition

- Any abnormal laboratory test results (hematology, clinical chemistry, or urinalysis) or other safety assessments (eg, ECG, radiological scans, vital signs measurements), including those that worsen from Baseline, considered clinically significant in the medical and scientific judgment of the Investigator (ie, not related to progression of underlying disease).
- Exacerbation of a chronic or intermittent pre-existing condition including either an increase in frequency and/or intensity of the condition.
- New conditions detected or diagnosed after study medication administration even though it may have been present before the start of the study.
- Signs, symptoms, or the clinical sequelae of a suspected drug-drug interaction.
- Signs, symptoms, or the clinical sequelae of a suspected overdose of either study medication or a concomitant medication. Overdose per se will not be reported as an AE/SAE unless it is an intentional overdose taken with possible suicidal/self-harming intent. Such overdoses should be reported regardless of sequelae.
- "Lack of efficacy" or "failure of expected pharmacological action" per se will not be reported as an AE or SAE. Such instances will be captured in the efficacy assessments. However, the signs, symptoms, and/or clinical sequelae resulting from lack of efficacy will be reported as AE or SAE if they fulfill the definition of an AE or SAE.

Events NOT Meeting the AE Definition

- Any clinically significant abnormal laboratory findings or other abnormal safety assessments which are associated with the underlying disease, unless judged by the Investigator to be more severe than expected for the participant's condition.
- The disease/disorder being studied or expected progression, signs, or symptoms of the disease/disorder being studied, unless more severe than expected for the study participant's condition.
- Medical or surgical procedure (eg, endoscopy, appendectomy): the condition that leads to the procedure is the AE.
- Situations in which an untoward medical occurrence did not occur (social and/or convenience admission to a hospital).
- Anticipated day-to-day fluctuations of pre-existing disease(s) or condition(s) present or detected at the start of the study that do not worsen.

10.3.2 Definition of serious adverse event

If an event is not an AE per definition above, then it cannot be an SAE even if serious conditions are met (eg, hospitalization for signs/symptoms of the disease under study, death due to progression of disease).

An SAE is defined as any untoward medical occurrence that, at any dose:
a. Results in death
b. Is life-threatening The term 'life-threatening' in the definition of 'serious' refers to an event in which the participant was at risk of death at the time of the event. It does not refer to an event, which hypothetically might have caused death, if it were more severe.
c. Requires inpatient hospitalization or prolongation of existing hospitalization In general, hospitalization signifies that the participant has been detained (usually involving at least an overnight stay) at the hospital or emergency ward for observation and/or treatment that would not have been appropriate in the physician's office or outpatient setting. Complications that occur during hospitalization are AEs. If a complication prolongs hospitalization or fulfills any other serious criteria, the event is serious. When in doubt as to whether "hospitalization" occurred or was necessary, the AE should be considered serious. Hospitalization for elective treatment of a pre-existing condition that did not worsen from baseline is not considered an AE.
d. Results in persistent disability/incapacity 
• The term disability means a substantial disruption of a person's ability to conduct normal life functions.• This definition is not intended to include experiences of relatively minor medical significance such as uncomplicated headache, nausea, vomiting, diarrhea, influenza, and accidental trauma (eg, sprained ankle) which may interfere with or prevent everyday life functions but do not constitute a substantial disruption.
e. Is a congenital anomaly/birth defect
f. Important medical events: 
• Medical or scientific judgment should be exercised in deciding whether SAE reporting is appropriate in other situations such as important medical events that may not be immediately life-threatening or result in death or hospitalization but may jeopardize the participant or may require medical or surgical intervention to prevent one of the other outcomes listed in the above definition. These events should usually be considered serious. Examples of such events include, but are not limited to, potential Hy's law, invasive or malignant cancers, intensive treatment in an emergency room or at home for allergic bronchospasm, blood dyscrasias or convulsions that do not result in hospitalization, or development of drug dependency or drug abuse.

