4.4.2 Data required for periodic data reviews

All available data at the time of the data cut-off will be included at each SDR. The database will not be locked, but the data should be as clean as possible, and it is not required to have resolved all queries prior to each database snapshot. Study enrollment will not be halted during planned IDMC review of the safety and efficacy data.

Required safety data to be used to support the SDR will include the following:

- Adverse events
- ECGs
- Vital signs
- Medical and procedure history
- Prior and concomitant medications
- Demographics
- Safety labs (hematology, chemistry, urinalysis)
- Total IgG
- Pregnancy
- Columbia-Suicide Severity Rating Scale (C-SSRS)

These data will be summarized using descriptive statistics. Data will also be provided in listings.

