8.2.2 Adverse events summaries

TEAEs will be summarized by the most recent dose level prior to onset of TEAEs and RLZ total, including the number and percentage of study participants and frequency. Additional details are described below:

1. Overview of TEAEs will include following categories: any TEAEs, serious TEAEs, participant discontinuation due to TEAEs, permanent withdrawal of IMP due to TEAEs,

temporary withdrawal of IMP due to TEAEs, TEAEs requiring dose change, treatment-related TEAEs, severe TEAEs, TEAEs leading to death, all deaths (AEs leading to death).

2. Incidence of TEAEs will be summarized by SOC, HLT, PT for:

- Any TEAEs
- Any TEAEs during Treatment Period
- Any TEAEs by maximum intensity (mild, moderate and severe)
- Any TEAEs by relationship
- Severe TEAEs
- Non-serious TEAEs above reporting threshold of 5% of study participants
- Fatal TEAEs
- Fatal TEAEs by relationship
- Serious TEAEs
- Serious TEAEs by relationship
- Participant discontinuation due to TEAEs
- TEAEs leading to permanent withdrawal of IMP
- TEAEs leading to temporary withdrawal of IMP
- TEAEs requiring dose change
- Treatment-emergent AESM
- Treatment-emergent AESI

3. Incidence of any TEAEs will be summarized by decreasing frequency of PT.

AESMs include severe headache, severe GI disorders (i.e., abdominal pain, diarrhea, vomiting), and opportunistic infection.

AESIs are the cases of potential Hy's Law (see [Section 8.3.1](#)).

AESMs and AESIs will be identified based on the assessment by the Investigator as recorded in the CRF. An AE will be counted as an AESM if there is a 'yes' response to the question "Adverse event of Special Monitoring?" and 'no' otherwise. An AE will be counted as an AESI if there is a 'yes' response to the question "Adverse Event of Special Interest?" and 'no' otherwise.

When applicable adverse event summaries will be ordered by alphabetical SOC, alphabetical HLT within SOC and decreasing frequency of PT in the RLZ total column for tables.

Listings of all TEAEs, all non-serious TEAEs, serious TEAEs, permanent withdrawal of IMP due to AEs, study participant discontinuation from study due to AEs, AEs leading to death, AESIs, AESMs will be presented by treatment group and participant. Persistent AEs and TEAE will be flagged in the listings. Most recent dose will be presented in listing even when the AE start date is partial.

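### A death classed as expected myasthenia gravis progression can be missing from the SAP's all-deaths row, because that row counts only adverse events leading to death

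*Protocol*

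**What the plan says.** Protocol 10.3.1 gives two rules that can apply to the same MG event. Among events that are AEs it lists "Exacerbation of a chronic or intermittent pre-existing condition including either an increase in frequency and/or intensity of the condition". Among events that are not AEs it lists "The disease/disorder being studied or expected progression, signs, or symptoms of the disease/disorder being studied, unless more severe than expected" for that participant. It also makes the clinical consequences of lack of efficacy reportable when they meet the AE or SAE definition. It does not say how expectedness is to be judged.

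Protocol 10.3.2 then sets a condition for SAEs, with examples: an event that fails the AE definition cannot be an SAE, "even if serious conditions are met (eg, hospitalization for signs/symptoms of the disease under study, death due to progression of disease".

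The primary safety endpoints are occurrence of TEAEs and of TEAEs leading to permanent withdrawal of study medication (SAP 2.2.1.1). The TEAE overview in SAP 8.2.2 ends with "TEAEs leading to death, all deaths (AEs leading to death". The death listing in the same section is a listing of AEs leading to death. The fatal categories in the SAP 5.1 summary of discontinuations are sub-categories of AE. The SAP plans no table or listing of deaths from any cause. The IDMC data list in SAP 4.4.2 has no separate item for deaths.

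**The concern.** A row labelled as all deaths should contain every death. Here a death must first be accepted as an AE, and the protocol names death from disease progression as an example of an event that may not be one. Anyone reading the overview table would take the row as a complete count.

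This matters because the study's main purpose is long-term safety, and the protocol itself describes MG as sometimes life-threatening (Protocol 1.1 and 2.1). Participants came from lead-in studies that required moderate to severe symptoms and consideration for IVIg or PEX (Protocol 4.2). One investigator could therefore call a crisis expected. Another could point out that Protocol 5.2 criterion 7 bars anyone in crisis or impending crisis at entry, and call a later crisis worse than expected. Both readings are defensible, so TEAE, SAE and death counts can depend on the site.

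**Working it through.** No arithmetic applies and the plan states no figure to reproduce. The check follows one fatal MG event through the definitions under each classification.

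1. Is it an AE? Protocol 10.3.1 says yes if it is treated as an exacerbation or as worse than expected, and no if it is judged expected progression.
2. Is it an SAE? Protocol 10.3.2 admits it only if step 1 was yes.
3. Where does it then appear?

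| Output | Source | What admits the event | Judged an AE | Judged expected progression |
|---|---|---|---|---|
| Primary endpoint and TEAE tables | SAP 2.2.1.1, 8.2.2 | A treatment-emergent AE | Present | Absent |
| 24-hour SAE reporting | Protocol 8.3.1, 10.3.2 | An AE that is serious | Present | Absent |
| All-deaths row and death listing | SAP 8.2.2 | An AE leading to death | Present | Absent |
| Fatal discontinuation categories | SAP 5.1 | Discontinuation due to an AE | Present | Absent |
| Primary reason for discontinuation | SAP 5.1 | Study termination form | Present | Present as a reason, not as a death count |
| Rescue summaries | SAP 6.4, 9.1.4 | IVIg or PEX given | If given | If given |

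The all-deaths row does drop the treatment-emergent restriction, since it stands beside the row for TEAEs leading to death. It keeps the AE restriction, and that is where the gap lies.

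The last two lines of the table are the only planned traces of a death on the right-hand path. The rescue endpoint in SAP 9.1.4 covers the Treatment Period only. SAP 6.4 summarises all rescue from Baseline onwards. Neither shows that the participant died. Protocol 10.3.3 has the investigator send the sponsor any post-mortem findings for a death during participation, but this produces no output.

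A hospitalised, non-fatal MG event follows the same two paths and is absent from the TEAE and serious TEAE tables on the second.

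No percentage is offered. SAP 8.2.2 tabulates by most recent dose before onset, with switching allowed. The 240 in SAP 3.9 is a maximum, and enrolment at a site stops once MG0007 is active there (Protocol 4.1). The row's denominators are therefore not fixed in the documents.

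**The case against.** The strongest reply is that the protocol does not exclude MG deaths as such. Section 10.3.2 is conditional, and 10.3.1 keeps in exacerbations, events worse than expected, and the consequences of lack of efficacy. It also excludes day-to-day fluctuation only when the condition does not worsen. Since participants in crisis are barred at entry, a fatal crisis should usually qualify as worse than expected. This stands against a reading that some will be tempted to make, that an MG hospitalisation or death can never be an SAE. The text does not say that. It does not remove the gap, because the SAE examples invite the opposite classification and the threshold is undefined.

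A reader might also infer that the IDMC would be blind to these events or to rescue use. The documents do not support this. SAP 4.4.2 includes concomitant medications and procedure history, states that all available data go to each review, and refers to efficacy data as well. Protocol 4.1 has the committee consider individual and cumulative cases, and its Charter is not among the documents. What stands is narrower: the list under "Required safety data to be used to support the SDR will include the following" names no deaths item.

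Nor can the point rest on every participant finishing with eight weeks off drug. Those who move to MG0007 from the Treatment Period use the PEOT visit as their end of study (Protocol 4.1).

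Finally, the protocol sends lack of efficacy to the efficacy scales on purpose. Making every serious MG worsening an SAE could turn inpatient rescue into SAEs and count one event under both safety and efficacy. That objection is fair. Such a redefinition is debatable, and correcting the deaths row does not need it.

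**Conclusion.** The concern holds in a limited form. If the plan is followed exactly, a death that the investigator attributes to expected MG progression can be left out of the all-deaths row, the death listing and the fatal discontinuation categories. A hospitalised MG event judged the same way can be left out of the primary TEAE results.

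The size is one missing count for each event so classified. How many there would be cannot be estimated, because the documents give no rate of MG death or crisis and no indication of how sites would classify one. The number may be zero, but a single omitted death would make the row's label untrue.

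The conclusion rests on two assumptions: that at least some investigators would apply the 10.3.2 example as written, and that the all-deaths row is programmed as its bracketed definition states. If the sponsor already takes deaths from another record, the SAP text should say so.

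**What to change.** 1. **SAP 8.2.2.** Derive the all-deaths row from every death recorded in the study, on the study termination form or any other record, whatever the cause and whether or not it is linked to an AE. Add a listing on the same basis. Keep the row for TEAEs leading to death as it is. Name the new listing in the IDMC data list in SAP 4.4.2.

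2. **Protocol 10.3.1 and 10.3.2.** Reconcile the exacerbation rule, the study-disease exclusion and the examples attached to the SAE condition, and define the threshold for worse than expected, so that all sites classify a fatal or hospitalised MG event in the same way.

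The cost is one redefined row, one more listing and a clarification of one appendix. The documents do not show a dedicated death form, so the sponsor should confirm which record carries the date and cause of death. The downside is small: the death count may be slightly less favourable than under the present definition.
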